5.4 Subject discontinuation from the study

Subjects will be informed that they are free to withdraw from the study at any time and for any reason.

The investigator may remove a subject from the study if, in the investigator's opinion, it is not in the best interest of the subject to continue the study. The investigator must remove a subject from the study if the subject experiences:

- A Serious Adverse Event the investigator defines as related to the study medication, regardless of the intensity of the event
- A non-serious adverse event the investigator defines as related to study medication that has a severity of severe and requires treatment to resolve.

Examples of other reasons subjects may be discontinued from the study are a change in compliance with an inclusion or exclusion criterion, occurrence of AEs, occurrence of pregnancy or use of a prohibited therapy. Notification of discontinuation will immediately (within 24 hours) be made to the study monitor.

All withdrawn subjects with ongoing AEs will be followed as appropriate.

The study may be discontinued at the discretion of NFllection. Some examples of reasons for discontinuation are the occurrence of the following:

- Increased frequency, severity, or duration of known AEs
- Medical, regulatory, or ethical reasons affecting the continued performance of the study
- Difficulties in the recruitment of subjects.

5.4.1 Screen Failures

A subject who consents to participate in the study but does not complete Visit 1 is considered a screen failure.

A minimal amount of screening failure information is required to ensure appropriate reporting of screen failures and to respond to queries from regulatory authorities. For detailed screening failure requirements please refer to the case report form (CRF) completion guidelines.

Subjects who are screen failures may be scheduled for a second Visit 1 (*i.e.*, rescreened) only after consultation of the Medical Monitor. If the subject will be rescreened, a new SI will be created. A subject may be rescreened only 1 time.

5.4.2 Randomization Failures

A subject who completes Visit 1 and is subsequently not randomized to study medication is considered a randomization failure.

A minimal set of CRFs is required to ensure appropriate reporting of subjects who are randomization failures. Detailed instructions for documenting subjects who are randomization failures will be included in the CRF completion guidelines.

5.4.3 Early Termination Visit

The investigator should complete the following study procedures for randomized subjects who prematurely discontinue from the study:

- For subjects who discontinue from the study prior to Visit 8, complete the Visit 8 procedures
- For subjects who complete Visit 8 and discontinue from the study prior to Visit 9 complete the Visit 9 procedures.

Detailed instructions for documenting subjects who prematurely discontinue from the study will be included in the CRF completion guidelines.

5.4.4 Lost to Follow-up

A subject who repeatedly does not attend scheduled visits and is unable to be contacted by the study site will be considered lost to follow-up.

The following actions for subjects who are lost to follow-up:

- The investigator or designee must attempt to contact the subject and reschedule the missed visit as soon as possible, must counsel the subject on the importance of maintaining the assigned visit schedule and must ascertain whether or not the subject wishes to and/or should continue in the study.
- Before a subject is deemed lost to follow up, the investigator or designee must make every effort to regain contact with the subject. These efforts should include where possible, 2 telephone calls and, if necessary, a certified letter to the subject's last known mailing address or local equivalent methods. These contact attempts should be documented in the subject's study file.
- Should the subject continue to be unreachable, she/he will be considered to have withdrawn from the study.

Detailed instructions for documenting subjects who are lost to follow-up will be included in the CRF completion guidelines.

5.5 Previous and Concomitant Therapies

5.5.1 Previous therapies

At Visit 1 and Visit 2, the investigator or designee will question the subject to ensure they have not used any excluded therapies.

5.5.2 Concomitant Therapies

Concomitant therapies are any new or existing therapy received from Visit 1 until discharge from the study.

Concomitant therapies include drug (*e.g.*, prescription, over-the-counter) and non-drug (*e.g.*, chiropractic, physical therapy, energy-based treatments) therapies. Subjects will refrain from receipt of any therapy in compliance with the inclusion/exclusion criteria and prohibited therapies (Section 5.5.3). Subjects should refrain from changing the use of any concomitant therapies during the study.

[figure not shown]
Any new or modified concomitant therapy must be recorded and considered to determine if it is related to an AE. An AE must be reported unless the therapy is modified for non-medical reasons (*e.g.*, health insurance purposes) or it is for prophylaxis (*e.g.*, vaccinations).

Do not report “PRN” (*i.e.*, as needed) as the frequency for a concomitant therapy. Report each time the therapy is used with a start date, end date and frequency.

5.5.3 Prohibited therapies

Subjects must not use any systemic therapy for cNF and must not use any topical cNF therapy on any Target cNF.

During this study, subjects are prohibited from using therapies listed in the exclusion criteria. Topical corticosteroids are not allowed to treat Target cNFs or within a 2cm margin of a Target cNF but may be used on non-Target cNF areas after consultation with and approval from the Medical Monitor (diagram not to scale).

The investigator should notify the Medical Monitor and the study monitor immediately (within 24 hours) if any prohibited therapies are required to ensure subject safety.

Subjects must avoid applying any topical product to any Target cNF for at least 6 hours after any study medication application.

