9.3.2 Analysis Populations and Missing-Data Imputation

All subjects who are randomized and dispensed study drug and have at least one post-baseline visit with efficacy evaluations will be included in the intent-to-treat (ITT) population.

Missing data imputation procedures based on the ITT population are described below. The Observed Cases (OC) population will include all subjects in the ITT population with observed efficacy data at Visit 8. No data imputation will be used with this population for subjects with missing data at any post-baseline visit.

The Observed Cases (OC) population will be used for primary and secondary efficacy analyses to address the main efficacy evaluation objective of the study. There will also be two sensitivity analyses of efficacy. For the first sensitivity analyses, the Per-Protocol (PP) population, drawn from the OC population subjects who completed the study through Visit 8 with no major protocol violations, will be used. For the second sensitivity analyses, the ITT population will be used, and all missing post-baseline efficacy data will be imputed using last observation carried forward (LOCF) from the last available observed efficacy data after the Baseline visit. Mixed Model-based missing data imputation or Multiple Imputation may be used as a supplementary imputation method. A supplemental efficacy analysis based specifically on subject Responders will also be conducted using the ITT population where subjects terminating the study before completing Visit 8 due to treatment-related adverse events will be imputed as Non-Responders. All efficacy analyses will perform separate

comparisons of each Active treatment group with the Vehicle group along with other contrasts described below. No adjustments for multiplicity will be made. All subjects who are randomized, received at least one confirmed dose of study drug, and have at least one post-baseline safety evaluation will be included in the Safety Population.

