9.3.5.3 Endpoints

The safety endpoint is to determine the safety of treatment with NFX-179 Gel ([REDACTED] and [REDACTED] or Vehicle Gel applied QD for 182 days of treatment. The results of dermal safety and local tolerability assessments including pain/burning, itching, erythema, edema, scabbing/crusting, and vesiculation/erosion will be summarized by treatment group and visit. The evaluation of adverse events will be based on summaries and listings of adverse events by treatment group, as described below under Safety Analyses. If tumor independence is confirmed as discussed above, the primary efficacy endpoint will be a dichotomized analysis conducted on the proportion of tumors achieving a reduction from baseline volume of at least 50%. A Chi-square analysis at the tumor level will be performed as the primary analysis between vehicle and each active treatment group. Otherwise, if tumor independence is not confirmed, the primary efficacy endpoint will be analyzed at the subject level. The primary efficacy analysis will then be a dichotomized Chi-square Responder analysis at the subject level. It will be based on the proportion of subjects considered to be Responders, where a Responder is defined as a subject

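### A Target cNF that received a prohibited or tumor-removing therapy and is at least 50% smaller at Visit 8 counts as a response in the primary analysis

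*Combined protocol and SAP*

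**What the plan says.** On conduct, section 5.5.3 bars the therapies listed in the exclusion criteria, any systemic cNF therapy, and topical cNF therapy on a Target cNF. It then provides for the case where they are nevertheless given: the investigator notifies the Medical Monitor and the study monitor within 24 hours "if any prohibited therapies are required to ensure subject safety". Section 5.4 lists, among reasons why a subject may be discontinued, "occurrence of AEs, occurrence of pregnancy or use of a prohibited therapy". Removal is mandatory only for a related SAE or for a non-serious event "related to study medication that has a severity of severe and requires treatment to resolve". Section 5.5.2 counts "chiropractic, physical therapy, energy-based treatments" among non-drug concomitant therapies and asks for dates and frequency, but not for the tumor treated.

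On analysis, section 9.3.2 states: "The Observed Cases (OC) population will include all subjects in the ITT population with observed efficacy data at Visit 8". It also states: "The Observed Cases (OC) population will be used for primary and secondary efficacy analyses". If tumor independence is confirmed, section 9.3.5.3 makes the primary analysis a "dichotomized analysis conducted on the proportion of tumors achieving a reduction from baseline volume of at least 50" percent. If the intraclass correlation is 0.25 or more, the subject-level analysis is primary and a Responder needs at least 5 tumors with that reduction. The one non-responder imputation is in a supplemental ITT analysis of subject Responders: "subjects terminating the study before completing Visit 8 due to treatment-related adverse events will be imputed as Non-Responders".

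**The concern.** The stated objective is the effect of the gel against vehicle. The entry criteria protect it before randomization: laser or other energy-based therapy on or near a Target cNF is excluded for 180 days before Visit 2 where the investigator judges that it impairs evaluation or adds unacceptable risk. Inclusion criterion 7 requires willingness to forego other treatment of every Target cNF. After randomization nothing in the analysis does the same job. If the event occurs and the tumor is measured, the responder rule credits the assigned gel with whatever the other therapy did. That biases the responder proportion in the arm where it happens, in the analysis that carries the efficacy conclusion.

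**Working it through.** **1. Following one tumor through the rules.** Suppose a Target cNF receives laser therapy in month 4 and flattens.

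- Sections 5.4 and 5.5.3: notification is required; the subject may stay.
- Section 5.6.9: all 10 Target cNFs are still evaluated at each visit, however often gel is applied.
- Section 7.2.1: a height below 0.5 mm is recorded as 0 mm. The volume formula is not stated, but any formula proportional to height then gives zero volume, a 100% reduction.
- Section 9.3.2: Visit 8 data exist, so the subject is in OC.
- Section 9.3.5.3: the reduction is at least 50%, so the tumor is a response.
- LOCF gives the same answer whenever the last observed value follows the therapy.
- The non-responder imputation does not apply, because its trigger is termination for a treatment-related AE.
- The Per-Protocol set might drop the subject. However, major protocol violations are not defined to include this use, section 12.4 defines violations only in general terms, and section 10.3 mentions an evaluability decision without criteria.

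**2. The plan's own figures.** 168 randomized 1:1:1 is 56 per arm, and 150 completers is 50 per arm; 1 − 150/168 = 10.7% loss. Power of at least 90% at two-sided 0.05 cannot be reproduced because both responder rates are redacted. All rates below are assumptions.

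**3. Tumor level.** Let p be the true vehicle response rate and f the fraction of vehicle tumors that are given other therapy and read as at least 50% smaller, independently of whether they would have responded. The vehicle rate rises by f × (1 − p). With p = 0.10 and 50 × 10 = 500 tumors per arm:

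- f = 1% (5 tumors): 0.01 × 0.90 = 0.9 points
- f = 3% (15 tumors): 0.03 × 0.90 = 2.7 points
- f = 5% (25 tumors): 0.05 × 0.90 = 4.5 points

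The difference from an active arm falls by the same amount if that arm has no such use.

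**4. Subject level.** One of 50 subjects reclassified is 1/50 = 2.0 points. With n = 50 per arm, d = p2 − p1 and p̄ = (p1 + p2)/2,

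power = Φ{[d − 1.96√(2p̄(1 − p̄)/n)] / √[p1(1 − p1)/n + p2(1 − p2)/n]}.

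Active rates were set to give 90% power without any other therapy. Example: p1 = 0.05 and p2 = 0.288 give (0.238 − 0.147)/0.071 = 1.28, power 0.90. One vehicle subject reclassified makes p1 = 0.07, giving (0.218 − 0.150)/0.0735 = 0.92, power 0.82.

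Power when k vehicle subjects are reclassified as Responders:

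| Vehicle / active | k=0 | 1 | 2 | 3 | 5 |
|---|---|---|---|---|---|
| 5% / 28.8% | 0.90 | 0.82 | 0.72 | 0.61 | 0.38 |
| 10% / 37.0% | 0.90 | 0.84 | 0.76 | 0.67 | 0.47 |
| 20% / 50.4% | 0.90 | 0.85 | 0.79 | 0.72 | 0.55 |

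Two-sided rejection rate with no drug effect, when k subjects in one active arm are reclassified (same formula plus the opposite tail):

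| Base rate | k=1 | 2 | 3 | 5 |
|---|---|---|---|---|
| 5% | 0.07 | 0.12 | 0.20 | 0.38 |
| 10% | 0.06 | 0.09 | 0.14 | 0.29 |
| 20% | 0.06 | 0.08 | 0.11 | 0.21 |

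These tables count subjects, not tumors. One affected tumor changes a subject's status only if it brings the number of responding tumors to 5. A systemic MEK or BRAF inhibitor could affect all 10 at once.

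**The case against.** The event may be rare. Section 5.5.3 speaks of therapies needed for safety, and elective removal of a benign tumor is not that. Criterion 7 and section 4.1 rule out other treatment of Target cNFs, and concomitant therapies are queried at every visit from Visit 2. Nothing in the documents shows that a therapy given for safety, such as a topical corticosteroid, halves a cNF. Analyzing outcomes as observed, with a Per-Protocol sensitivity analysis, is also a recognized choice. All of this bears on frequency and on the choice of estimand. It does not supply a rule for the tumor when the event occurs, and the plan nowhere says that it intends to count response regardless of other therapy.

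A reader might infer more than the documents support:

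- *That treatment of any event leads only to optional discontinuation.* Section 5.4 makes removal mandatory for a related SAE and for a severe related event needing treatment. Rescue is not a protocol term.
- *That the investigator's decision to discontinue settles whether the tumor is in or out.* Under section 5.4.3, subjects who leave before Visit 8 complete the Visit 8 procedures. Whether those data count as Visit 8 data for OC is not stated.
- *That the bias has a known direction.* More use in vehicle and more use in active are both conceivable, with opposite effects.

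**Conclusion.** The point holds on the text. The OC definition and the responder rule together score a tumor reduced by another therapy as a response to the assigned gel, and no other primary-analysis rule prevents it. The size is unknown. The 0.9 to 4.5 points at tumor level, and the power and rejection figures at subject level, rest on assumed response rates and an assumed number of affected tumors or subjects in one arm only. They show that a few reclassified subjects in 50 would matter, not that this many are expected.

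**What to change.** - In sections 9.3.2 and 9.3.5.3, state that a Target cNF is a non-responder in the primary OC and the ITT responder analyses if, before Visit 8, it received laser or other energy-based therapy, excision, or a prohibited topical on that tumor. Name excision explicitly, because the exclusion list does not. For a prohibited systemic therapy (MEK or BRAF inhibitor, or retinoid), all 10 tumors are non-responders.
- Exclude from the rule topical products that sections 5.6.8 and 5.9 permit outside the 6-hour windows. Apply the 2 cm margin only to topical corticosteroids, as section 5.5.3 does.
- Keep the as-observed analysis as a sensitivity analysis.
- State whether early-termination Visit 8 data enter OC, and whether such therapy is a major protocol violation for the Per-Protocol set.
- Record the Target cNF number with each such therapy. The CRF is not among the documents, so it may already do this.

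The cost is about a paragraph of text and at most one data item. The downside is that a tumor already responding before the other therapy counts as a failure. That could fall unevenly across arms, so report the number of affected tumors by arm.

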5.6 Study Medications

The study medications are faint yellow, clear gels and are indistinguishable in physical appearance. Study medications must be maintained in a secure area with limited access under appropriately controlled and monitored storage conditions at each investigational center.

5.6.1 Study medication identity

Study Medication Information			
Name	NFX-179 Gel ■	NFX-179 Gel ■	NFX-179 Gel Vehicle
Manufacturer	MedPharm Limited [name]		
Active ingredient	■		None
Active concentration	■	■	0%
Storage conditions	59°F to 77°F (15°C to 25°C)		

The investigator or designee must confirm appropriate storage temperature was maintained during shipment for all study medication received and any discrepancies must be reported to NFlection and resolved before the study medication is dispensed.

5.6.2 Study medication packaging and labeling

The study medications will be packaged in identical appearing white glamine tubes that each contain ■ (g) of study medication.

One Subject Kit that contains 5 tubes of study medication in two separate cartons of 3 and 2 tubes, respectively, will be prepared for each subject.

At a minimum, each carton will be labeled with a two-part, three-panel label. One part of the label remains affixed to the Subject Kit and the second part, a two-panel tear-off, is separated when the Subject Kit is first dispensed to the subject. The affixed label part and the first panel of the tear-off label part show at least the following:

- Subject Kit number (Subject Kit number is also the randomization number)
- Protocol number
- Space to enter the SI
- Space to enter the date randomized
- Storage conditions
- NFlection information.

The second panel of the tear-off part is a blinded label (*e.g.*, scratch-off panel or equivalent) which when opened identifies the study medication in the Subject Kit. The blinded label should be opened only in a medical emergency.

At a minimum, study medication tubes will be labeled with a one-part label that remains attached to the tube and shows at least the following:

- Subject Kit number
- Protocol number
- Tube number
- Space to enter the SI
- Space to enter the date dispensed
- Directions for use
- Investigational drug warning.

5.6.3 Method of study medication assignment

Prior to the study start NFlection, or a designated third party, will generate a list of randomization numbers that will be provided to the assigned vendor for study medication labeling. The randomization number is also the Subject Kit number.

The randomization list will be stored with access limited to the appropriate personnel for the study medication labeling. The randomization list will be made available as appropriate to unblind the database.

5.6.4 Subject randomization

At Visit 2, the investigator will determine the subject's eligibility for randomization to study medication. To be eligible for randomization the subject must:

- Have a PTA ≥ 2 for all Target cNFs
- Have clinical laboratory test results for all measured analytes at Visit 1 and all results are either within the range of normal for the laboratory or, any abnormal results, are defined as Not Clinically Relevant (NCR) by the investigator.
- Have, if a Woman of Childbearing Potential (WOCBP), a negative urine pregnancy test result at Visit 2.
- Have NOT used any topical or system therapies within the specified period prior to Visit 2 per the exclusion criteria

The investigator or designee will assign study medication to eligible subjects by selecting the

Subject Kits in chronological sequence in ascending numerical order starting with the lowest available Subject Kit number. The investigator will not omit or reuse any Subject Kit number.

5.6.5 Dispensing and collecting study medication

The study medication must be dispensed only to study subjects, only at investigational centers specified on the Form FDA 1572 (or its equivalent) and only by authorized personnel as required by applicable regulations and guidelines.

At Visit 2, after a subject is randomized, locate the Subject Kit with the lowest available number and complete the label. Next locate the unused study medication tube with the lowest available number and complete the label. Weigh the study medication tube. Dispense one study medication tube to the subject. Observe the subject apply a thin layer of study medication to each cNF tumor. Weigh the study medication tube post subject application of study medication.

At Visits 3-7, examine the study medication tube(s) dispensed to the subject, weigh the tube(s), return tubes that contain, in the investigational staff member's opinion, useable study medication to the subject and collect tubes that contain no useable study medication. Dispense a new tube of study medication, if required for treatment until the next visit, following the instructions above. A subject should not possess more than 2 tubes of study medication at one time.

At Visit 8, collect all study medication tubes from the subject and weigh each tube.

The subject must bring all dispensed study medication tubes with them to all visits.

The investigational center staff member should make every effort to obtain all dispensed and unused study medication. Two documented telephone contacts followed by a registered letter to the subject are adequate follow-up efforts. If these efforts fail, the reason for the failure must be noted on the appropriate line of the study medication inventory CRF.

All unused and un-dispensed study medication should be held for inspection by NFlection's study monitor. Upon completion of the study all study medication will be returned to NFlection or a designated third party by the study monitor using a traceable method unless returned study

medication is destroyed by the site according to applicable SOP.

5.6.6 *Weighing study medication*

An investigational center staff member will weigh each study medication tube when dispensed, at each study visit, and when returned using the provided scale (or equivalent). The study medication container weight must be reported to the nearest 0.1 g. The study medication tubes must be weighed with the label attached and the cap on and without any other packaging.

At Visit 2, the study medication tube dispensed to the subject must be weighed pre subject application of study medication and post subject application of study medication.

The scale used to weigh the study medication tubes must be calibrated, according to the instructions provided for the scale, and the calibration documented, each day the scale is used, prior to use. Any scale that does not pass the calibration test must not be used to weigh the study medication.

5.6.7 *Route of Administration, frequency and treatment period*

The study medications are applied topically to each Target cNF, once daily for 182 days (26 weeks).

5.6.8 *Study medication application*

The study medications are for external, topical use on each Target cNF only and on the appropriate study subject only.

To perform a study medication application the subject should:

- Wash her/his hands before starting the application
- Avoid applying the study medication to any open wounds or obviously infected skin
- Apply an amount of the assigned study medication sufficient to cover each Target cNF with a thin layer of the study medication
- Gently rub in the study medication until no visible accumulation is evident
- Wash her/his hands after completing the application.

The subject must apply study medication to the entire area of each Target cNF limiting exposure to the un-affected skin surrounding the cNF.

At Visit 2, an investigational center staff member will instruct the subject on the proper application technique and observe the subject's study medication application to ensure proper

application technique and record the time the subject completes the application to the last Target cNF as the Application Completion Time. A staff member will monitor the subject for adverse events for at least 20 minutes after the Application Completion Time.

Subjects should continue QD application of the assigned study medication to each Target cNF for 182 days (26 weeks) with 18-30 hours between applications.

Subjects should not apply the study medication within 6 hours prior to a study visit, except on Visit 4 when the subject should apply study medication 4 (\pm 2 hours) prior to the scheduled appointment time. Record the study medication application time on the day of Visit 4.

If during the treatment phase a Target cNF clears (*i.e.*, PTA grade of 0) instruct the subject to continue QD application to the area of the cNF for the remainder of the treatment period.

After completing a study medication application, a subject should not:

- Wash or submerge any Target cNF for at least 6 hours
- Apply any topical products (*e.g.*, cosmetics, emollient/moisturizer, sunscreens) to any Target cNF for at least 6 hours.

At Visits 3-7 review the application technique with the subject to ensure they are performing the application properly, are using an appropriate amount of study medication and are applying the study medication to the correct cNFs.

